9.6. Procedure for Breaking the Blind for Individual Participants

Not applicable to this study.

9.7. Follow-up of Adverse Events

9.7.1. Follow-up of Nonserious Adverse Events

Nonserious AEs that are identified on or before the last scheduled visit (Day 51 or EWV) must be followed through and recorded on the AE eCRF. All nonserious events that are ongoing at Day 51 or EWV will be recorded with the current status noted as “Not Recovered/Not Resolved” on the AE eCRF. The status of ongoing, previously reported AEs will be reviewed at the Day 51/EWV to determine if resolved. For participants that continue in the study beyond Day 51, the

AV7909 Anthrax Vaccine
IND 014451
Protocol EBS.AVA.210, Version 3.0 (28 October 2019)

status of ongoing AEs will be queried at the quarterly phone contacts to determine status and update the resolution status in the AE eCRF.

9.7.2. Follow-up of Serious Adverse Events or Adverse Events of Special Interest

Participants experiencing SAEs or AESIs will be followed clinically until their health has returned to normal and all parameters have returned to baseline or has otherwise been explained or they have been referred to outside care. It is expected that the PI or designee will provide or arrange appropriate supportive care for the participant. Withdrawals of participants from treatment and/or the trial are at the discretion of the PI or designee, according to the guidance provided in [Section 7.3](#).

All SAEs/AESIs will be followed by the PI or designee until one or the other condition is met:

- The SAE/AESI is resolved or stable if expected to remain chronic.
- The participant is referred to a specialist or other physician for treatment and follow-up. The PI or designee will follow events even if the participant is seen by another physician. The PI or designee will follow-up with the participant and the participant's physician to obtain information about the event outcome and any treatments and medications administered for the event.

The following will be considered acceptable reasons for discontinuation of follow-up of ongoing SAEs/AESIs:

- Participant withdraws consent.
- Participant is referred to appropriate long-term medical care.
- Participant is considered lost to follow-up (refer to [Section 7.4](#) for description of contact attempts before a participant may be deemed lost to follow-up).

It is expected that the clinical site will obtain supporting medical records from appropriate physicians and record this information on the SAE/AESI Report Form (refer to [Section 9.3](#)) and AE eCRF. Additional information received related to any SAE/AESI must be forwarded within 24 hours of awareness to the Emergent Global PV Department.

10. STATISTICAL ANALYSIS

10.1. Study Endpoints and Statistical Hypotheses

10.1.1. Primary Endpoints

To assess whether co-administration of AV7909 with antibiotics affects antibiotic PK profiles, equivalence tests on the PK parameters (AUC_{0-12h} and C_{max}) at steady state pre- and post-vaccination will be carried out separately for ciprofloxacin and doxycycline using PK data collected from subjects from independent study groups (Group 1 for ciprofloxacin, Group 2 for doxycycline).

For each of the primary endpoints (for each of the two antibiotics), the equivalence tests on PK parameters (AUC_{0-12h} and C_{max}) at steady state pre- and post-vaccination will be performed. Therefore, demonstration of non-interference of steady state PK is defined separately for each antibiotic and there is only one way to meet the primary endpoint for each antibiotic.

Specifically, for each antibiotic, the null hypotheses are:

- AUC_{0-12h} : The geometric mean of the within-participant ratios of post-vaccination (Day 35 for ciprofloxacin and Day 38 for doxycycline) over the pre-vaccination (Day 8) AUC_{0-12h} will be greater than 1.25 or less than 0.80.
- C_{max} : The geometric mean of the within-participant ratios of the post-vaccination (Day 35 for ciprofloxacin and Day 38 doxycycline) over the pre-vaccination (Day 8) C_{max} will be greater than 1.25 or less than 0.80.

The null hypothesis will be rejected when the 90% confidence intervals (CIs) of the geometric mean of the within-participant ratios is contained entirely within the equivalence bounds of [0.8, 1.25]. For each antibiotic, to conclude that administration of two-dose regimen of AV7909 does not affect the steady state of PK profile, the null hypotheses should be rejected for both endpoints AUC_{0-12h} and C_{max} .

10.1.2. Secondary Endpoints

10.1.2.1. Secondary Safety Endpoints

- Incidences of AEs from the first dose of any IP through the Final Study Visit (Day 51 ± 1 d)
- Incidences of serious AEs (SAEs) from the first dose of any IP until the 12-month follow up (Day 388 ± 14 d)
- Incidences of solicited systemic and injection site reactions reported in participant e-diaries following each vaccination
- Incidences of AESIs from the first dose of any IP until the 12-month follow up (Day 388 ± 14 d)
- Incidences of clinical laboratory abnormalities

No hypothesis testing is planned for any of the safety endpoints.

AV7909 Anthrax Vaccine

IND 014451

Protocol EBS.AVA.210, Version 3.0 (28 October 2019)

10.1.2.2. Secondary Pharmacokinetic Endpoints

To determine if the single-dose PK values of either ciprofloxacin or doxycycline are affected by AV7909 vaccination, separate equivalence tests will be carried out in parallel for each antibiotic in the similar manner as the primary PK analyses:

- AUC_{0-12h} : Geometric mean of within-participant ratios of post-vaccination (Day 31 for ciprofloxacin and Day 32 for doxycycline) over the pre-vaccination (Day 4 for ciprofloxacin and Day 2 for doxycycline) AUC_{0-12h} is greater than 1.25 or less than 0.8.
- C_{max} : Geometric mean of within-participant ratios of post-vaccination (Day 31 for ciprofloxacin and Day 32 for doxycycline) over the pre-vaccination (Day 4 for ciprofloxacin and Day 2 for doxycycline) C_{max} is greater than 1.25 or less than 0.8.

No hypothesis testing is planned for the secondary PK endpoints, which will be evaluated and reported for information only.

10.1.2.3. Secondary Immunogenicity Endpoints

To evaluate whether the co-administration of antibiotics affects the immune response after two IM doses of AV7909, a non-inferiority test will be conducted independently for ciprofloxacin and doxycycline. Specifically, the null hypotheses are:

- For ciprofloxacin: the geometric mean ratio of TNA NF_{50} values at Day 37 for Group 1 over Group 3 will be less than or equal to 0.5
- For doxycycline: the geometric mean ratio of TNA NF_{50} values at Day 37 for Group 2 over Group 3 will be less than or equal to 0.5

The null hypothesis will be rejected when the lower bound of the two-sided 95% CI of the geometric mean ratio of TNA NF_{50} values is greater than 0.5.

For each antibiotic, the formal hypothesis testing for the secondary immunogenicity endpoints will only be carried out after the primary PK endpoint has been met for the corresponding antibiotic. If the primary PK endpoint for an antibiotic is not met, the corresponding secondary immunogenicity endpoints will be provided for information only.

10.2. Sample Size and Power

The sample size for this study was selected based on both the primary and secondary endpoints.

The assessment as to whether vaccination with AV7909 affects the PK of either ciprofloxacin or doxycycline will be made based on the geometric mean of the within-participant ratios (post-vaccination over pre-vaccination) of AUC_{0-12h} and C_{max} . The equivalence margin for the geometric mean ratio is [0.80, 1.25], which will be compared with the 90% CI for the geometric mean of within-participant ratios of AUC_{0-12h} and C_{max} . Assuming the coefficient of variation (CV) is 30% for geometric mean ratio and the true geometric mean ratio is 0.95, 27 participants allow for 90% power to reject the null hypothesis at a significance level of 5%. A group size of 40 participants for Group 1A (AV7909 + ciprofloxacin with PK) or Group 2A (AV7909 +

AV7909 Anthrax Vaccine
IND 014451
Protocol EBS.AVA.210, Version 3.0 (28 October 2019)

doxycycline with PK) is planned to allow for up to 30% of participants being excluded from the PK population.

A sample size of 53 in each of the IP groups (Group 1 = AV7909 + ciprofloxacin, Group 2 = AV7909 + doxycycline, Group 3 = AV7909 only) provides 90% power at the 2.5% one-sided significance level for the non-inferiority test, defined as the lower bound of the two-sided 95% CI of the geometric mean ratio of the AV7909 + antibiotic over the AV7909 only (Group 1 vs. Group 3, Group 2 vs. Group 3) greater than 0.5. This assumes that the true geometric mean ratio between the two groups is 0.85 and the CV of TNA NF₅₀ values in each group is 100%. A total of 70 per IP group is planned to allow for up to 25% of drop-out rate.

The sample size calculation was performed using SAS 9.4 statistical software.

10.3. Analysis Populations

There will be four analysis populations for this study:

The Intent-to-treat (ITT) Population will include all participants who are randomized. Participant disposition and baseline demographics will be summarized by IP group (Groups 1, 2 and 3) for the ITT population according to the group into which the participant is randomized.

The Safety Population will include all randomized participants who receive at least one dose of either antibiotic or AV7909. All the safety analyses will be conducted with the Safety Population according to the treatment they received.

The PK Population will include all participants in Group 1A and Group 2A who:

- Received two doses of AV7909 according to the protocol (eg, correct dose no temperature excursion, and within the study-specified windows)
- If in Group 1A, received at least 5 of the 7 in-clinic ciprofloxacin doses between Day 4 through the morning of Day 8 and between Day 31 through the morning of Day 35; or if in Group 2A, received at least 7 of the 9 in-clinic doxycycline doses between Day 2 through the morning of Day 8 and between Day 32 through the morning of Day 38
- Have adequate data for PK analysis for the calculation of AUC_{0-12h} and C_{max} at the Day 8 (both Group 1A and 2A) and Day 35 (Group 1A) or Day 38 (Group 2A) visits,
- Have no protocol deviations that would affect ciprofloxacin or doxycycline PK

Exclusion of participants from population will be done on a case-by-case basis at the time of the PK parameter analysis.

The PK Population will be used for all PK analyses. Participants will be included in the treatment group (ciprofloxacin or doxycycline) according to the antibiotic they received.

The Immunogenicity Population will include all randomized participants who meet the following criteria:

- Received two AV7909 vaccinations according to the protocol (eg, correct dose, no temperature excursion, and within the study-specified windows)

AV7909 Anthrax Vaccine

IND 014451

Protocol EBS.AVA.210, Version 3.0 (28 October 2019)

- Had a valid immunogenicity (TNA) result at Day 1 (pre-vaccination) showing no evidence of previous exposure to anthrax or an anthrax vaccine (ie, TNA below the limit of detection)
- Had a valid immunogenicity (TNA) result at Day 37, within the study specified window
- Participants in Group 1 or 2 should have taken at least 50% of the protocol-specified antibiotic doses

The Immunogenicity Population will be used for the immunogenicity analyses. Participants will be included in the IP group (Group 1, 2 and 3) according to the treatment they actually received.

10.4. Handling of Outliers and Missing Data

Individual serum concentrations or entire serum concentration-time profiles for a participant may be excluded from the analysis at the discretion of the pharmacokineticist following a review of available documentation (eg, bioanalytical report, validation report, protocol deviation log) and communication with the sponsor. Any such exclusion will be clearly listed in the clinical study report along with justification for exclusion. Any excluded outlier data should be flagged in the individual data listings.

Missing PK samples or antibiotic concentration values or missing immunogenicity response TNA NF₅₀ values will be handled as described in the Statistical Analysis Plan (SAP). Antibiotic concentrations reported as below the lower limit of quantification (< LLOQ) will be handled as specified in the SAP. Non-missing TNA NF₅₀ values reported as < LLOQ will be handled as specified in the SAP.

10.5. Statistical Methods

10.5.1. PK Analyses

10.5.1.1. Summary of Concentrations and PK Parameters

Summary statistics for serum concentrations of ciprofloxacin and doxycycline will be tabulated by time point and study day. Summary statistics will be provided for trough concentrations of ciprofloxacin and doxycycline by study day. The PK parameters shown in [Table 11](#) will be derived from the concentration-time data by noncompartmental analysis methods and summarized by study day.

Table 11 Antibiotic Pharmacokinetic Parameters

Variable	Definition
C _{max}	Maximum observed serum concentration
t _{max}	Time of maximum observed serum concentration
t _{1/2}	Elimination half-life (calculated as ln 2/ K _{el})
K _{el}	Elimination rate constant

AV7909 Anthrax Vaccine

IND 014451

Protocol EBS.AVA.210, Version 3.0 (28 October 2019)

Variable	Definition
AUC _{0-12h}	Area under the serum concentration-time curve (12 hours)
AUMC	Area under the first moment curve
AUC _{0-inf}	Area under the serum concentration-time curve extrapolated to infinity
MRT	Mean residence time

10.5.1.2. Equivalence Testing for Primary PK Endpoints

The goal of the study with the primary PK endpoints is to demonstrate that vaccination with AV7909 does not affect the steady-state PK profiles of either ciprofloxacin or doxycycline. The equivalence testing will be constructed using paired two one-sided t-tests (TOST) to provide the point estimate and 90% CIs for geometric mean of the within-participant ratios of the steady-state values of AUC_{0-12h} and C_{max} post two doses of AV7909 (Day 35 for ciprofloxacin and Day 38 for doxycycline) vs. pre-vaccination of AV7909 (Day 8 for ciprofloxacin and doxycycline). To conclude that AV7909 vaccine has no effect on the steady state PK for ciprofloxacin or doxycycline, the 90% CIs should fall entirely within the equivalence range of [0.80, 1.25] for both endpoints AUC_{0-12h} and C_{max}.

To demonstrate that antibiotic concentrations have achieved steady state, the trough value analysis will be performed using the stepwise testing for linear trend, the application of the NOSTASOT (No Statistical Significance Of Trend) methodology proposed by {[Maganti et al, 2008](#)}. The details of the calculation will be provided in the SAP.

10.5.1.3. Equivalence Testing for Secondary PK Endpoints

The secondary PK analyses will be performed to evaluate the effect of vaccination with AV7909 on the single-dose PK profile for either ciprofloxacin or doxycycline. The equivalence tests will be conducted in a similar statistical manner as the primary analyses. If the 90% CIs for geometric mean of the within-participant ratios of the single-dose values of AUC_{0-12h} and C_{max} post two doses of AV7909 (Day 31 for ciprofloxacin and Day 32 for doxycycline) vs. pre-vaccination of AV7909 (Day 4 for ciprofloxacin and Day 2 for doxycycline) fall entirely within the equivalence range of [0.80, 1.25] for both endpoints, AUC_{0-12h} and C_{max}, it will be concluded that the AV7909 vaccine has no effect on the single dose PK for ciprofloxacin or doxycycline.

10.5.2. Non-Inferiority Testing for Secondary Immunogenicity Endpoints

Two-sided 95% CIs will be calculated for the geometric mean ratio of TNA NF₅₀ values at Day 37 between the AV7909 + antibiotic group and the AV7909 only group (Group 1 vs. Group 3, Group 2 vs. Group 3). To conclude that ciprofloxacin or doxycycline does not reduce the immune response to AV7909, the lower bound of the 95% CI should be greater than the non-inferiority margin of 0.5.

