To evaluate whether the administration of ciprofloxacin affects the immunogenicity of AV7909, TNA NF_{50} values two weeks after the second dose of AV7909 will be compared between the cohort of participants that received both ciprofloxacin and AV7909, ie, Group 1, also known as the ciprofloxacin test cohort, and the cohort who received AV7909 only, ie, Group 3 or the reference cohort. Point estimates and two-sided 95% lower CIs will be constructed for the ratio (test: reference) of geometric means. If the lower bound of the two-sided 95% lower CI is greater than 0.5 (the non-inferiority margin) it can be concluded that the immune response in the cohort who received AV7909 plus ciprofloxacin is non-inferior to the cohort which received AV7909 alone and thus that ciprofloxacin did not demonstrably affect the immunogenicity of AV7909.

The same evaluation will be conducted to determine if the administration of doxycycline affects the immunogenicity of AV7909 in that TNA NF_{50} values two weeks after the second dose of AV7909 will be compared between the cohort of participants that received both doxycycline and AV7909, ie, Group 2, the doxycycline test cohort, and the cohort who received AV7909 only (ie, Group 3 or the reference cohort). Point estimates and two-sided 95% lower CIs will be constructed for the ratio (test: reference) of geometric means. If the

AV7909 Anthrax Vaccine

IND 014451

Protocol EBS.AVA.210, Version 3.0 (28 October 2019)

lower bound of the two-sided 95% lower CI is greater than 0.5 (the non-inferiority margin) it can be concluded that the immune response in the cohort who received AV7909 plus doxycycline is non-inferior to the cohort which received AV7909 alone and thus that doxycycline did not demonstrably affect the immunogenicity of AV7909.

Sample Size Considerations

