10.8. Multiplicity

In this phase 2 study, multiplicity adjustment is not planned. All the PK and immunogenicity endpoints are evaluated in parallel for the two antibiotics, ciprofloxacin and doxycycline.

The primary PK endpoints for each antibiotic will be met when the 90% CIs of the geometric mean of ratios for both AUC_{0-12h} and C_{max} are contained entirely within the equivalence bounds of [0.8, 1.25]. Since both parameters must satisfy the equivalence condition and each equivalence test is conducted at 5% level, the overall type I error rate is controlled at less than 5%.

For immunogenicity, non-inferiority is evaluated as a one-sided test at 2.5% level. As a secondary endpoint, the test will only be formally evaluated when the corresponding primary PK endpoints have been met. Otherwise the results will be provided for information. No adjustment for multiplicity is required based on the closed test procedure.

No other formal hypothesis testing will be carried out. The secondary PK endpoints (single dose) will be evaluated and reported for information only.

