### 2.3.2.3 Secondary Immunogenicity Endpoints

For each antibiotic, to evaluate whether the co-administration of the antibiotic affects the immune response after two IM doses of AV7909, a non-inferiority test will be conducted.

Specifically, the null hypotheses are:

- For ciprofloxacin: the geometric mean ratio of TNA  $NF_{50}$  values at Day 37 for Group 1 over Group 3 is less than or equal to 0.5

- For doxycycline: the geometric mean ratio of TNA NF50 values at Day 37 for Group 2 over Group 3 is less than or equal to 0.5

The null hypothesis is rejected when the lower bound of the two-sided 95% CI of the geometric mean ratio of TNA NF50 values is greater than 0.5.

For each antibiotic, the formal hypothesis testing for the secondary immunogenicity endpoints will only be carried out after the primary PK endpoint has been met for the corresponding antibiotic. If the primary PK endpoint for an antibiotic is not met, the corresponding secondary immunogenicity endpoints will be provided for information only.

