## 7.2 Secondary Immunogenicity Endpoints

The secondary immunogenicity analysis is aimed to assess whether the immunogenicity of AV7909 two weeks following the final dose of a two-dose vaccination series is affected by concomitant dosing with oral ciprofloxacin or doxycycline.

Non-inferiority test will be constructed using the GMT ratio of TNA NF50 (Group 1/Group 3 or Group 2/Group 3) between IP group with participants that received both AV7909 and ciprofloxacin or doxycycline (Group 1 or 2) and the IP group with participants that received AV7909 only (Group 3). Point estimate and the 95% CI for the GMT ratio will be estimated using the linear regression based on log10 transformed TNA NF50 with equal variance. If the lower bound of the two-sided 95% CI of geometric mean ratio is greater than the non-inferiority margin of 0.5, it is concluded that the immune response in the group who received AV7909 plus either ciprofloxacin or doxycycline is non-inferior to the group which received AV7909 alone and thus that either ciprofloxacin or doxycycline did not demonstrably affect the immunogenicity of AV7909.

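### Passing the 0.5 non-inferiority margin is allowed to mean that the antibiotic does not reduce the TNA response, even when the 95% CI lies wholly below 1

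*Protocol*

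**What the plan says.** The null hypothesis is stated precisely. Protocol 10.1.2.3 puts it, for ciprofloxacin, as the geometric mean ratio of TNA NF50 "values at Day 37 for Group 1 over Group 3 will be less than or equal to 0.5", with the matching statement for Group 2 over Group 3. SAP 2.3.2.3 agrees. The null is rejected when the lower limit of the two-sided 95% CI exceeds 0.5.

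The conclusions drawn from that rejection are wider:

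- Protocol 10.5.2: "To conclude that ciprofloxacin or doxycycline does not reduce the immune response to AV7909", the lower limit should exceed the margin of 0.5. The word non-inferior is not part of the conclusion.
- Protocol synopsis, ciprofloxacin: non-inferior, "and thus that ciprofloxacin did not demonstrably affect the immunogenicity of AV7909".
- Protocol synopsis, doxycycline: non-inferior, and "thus that doxycycline did not demonstrably affect the immunogenicity of AV7909".
- SAP 7.2: non-inferior, and "thus that either ciprofloxacin or doxycycline did not demonstrably affect the immunogenicity of AV7909".

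Neither document sets a condition on the upper limit or says how to word a result whose CI lies wholly below 1. The test is formal only if the same antibiotic's primary PK endpoint is met; otherwise "the corresponding secondary immunogenicity endpoints will be provided for information only" (SAP 2.3.2.3).

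**The concern.** Rejecting a null of 0.5 or less supports one statement: the response has not been halved or worse. It does not support a statement that there is no reduction, and it does not support a statement that no effect was demonstrated. A 95% CI that lies wholly between 0.5 and 1 meets the plan's condition and at the same time contradicts both conclusions, because an interval that excludes 1 from below is a demonstrated reduction.

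What is at stake is the claim that the report may make. Whether either antibiotic impairs the response is the question behind the secondary immunogenicity objective, so this sentence would be a headline result. The data, the test and the margin are not in question, and nothing here implies that a ratio in this range means lost protection.

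**Working it through.** **Inputs.** From Protocol 10.2 and SAP 2.4: 53 evaluable per group, 70 planned, CV 100%, true ratio 0.85, 90% power, one-sided 2.5%. From Protocol 10.5.2: margin 0.5 and a two-sided 95% CI. From SAP 7.2: linear regression on log-transformed NF50 with equal variance. I take this as a two-group comparison with t on 2n − 2 degrees of freedom and log-normal NF50.

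**1. Reproduce the plan's sample size.** SD on the natural-log scale = √ln(1 + CV²) = √ln 2 = 0.8326. Distance from the true ratio to the margin = ln 0.85 − ln 0.5 = 0.5306. The noncentral t gives 90.2% power at 53 per group and 89.6% at 52. The plan's 53 is therefore reproduced, and this is the model behind it.

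**2. Half-width of the CI on the log scale.** h = t(0.975, 2n − 2) × SD × √(2/n).
- n = 53: 1.983 × 0.8326 × 0.1943 = 0.3207
- n = 70: 1.977 × 0.8326 × 0.1690 = 0.2783

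**3. The range of observed ratios that passes with a CI wholly below 1.** The lower limit exceeds 0.5 if the ratio is above 0.5·e^h. The upper limit is below 1 if the ratio is below e^(−h).

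| Evaluable per group | 0.5·e^h | e^(−h) | Range, rounded inward |
|---|---|---|---|
| 53 | 0.6891 | 0.7256 | 0.690–0.725 |
| 70 | 0.6604 | 0.7571 | 0.661–0.757 |

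Check at n = 53: an observed 0.690 gives a CI of 0.501–0.951, 0.70 gives 0.508–0.965, and 0.725 gives 0.526–0.999. At n = 70, 0.70 gives 0.530–0.925.

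**4. How often this happens.** The table gives the probability per antibiotic at a true ratio of 0.85, given that the PK endpoint is met. It allows for sampling variation in the pooled SD (chi-square).

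| True CV | n = 53 | n = 70 |
|---|---|---|
| 75% | 21.8% | 29.4% |
| 100% (plan) | 7.2% | 17.1% |
| 112% | 2.5% | 11.7% |
| 125% | 0.5% | 6.3% |

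A simulation of 200,000 trials with the control group shared between the two comparisons, at CV 100%, gives 7.4% and 7.3% for the two antibiotics at n = 53, and 17.1% and 17.2% at n = 70. If the true ratio were 0.70, the figures at CV 100% would be 13.6% and 37.2%.

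**5. Where the range closes.** It is empty once 0.5·e^h ≥ e^(−h), that is, h ≥ ln(2)/2 = 0.3466. Solving for the CV gives 111.7% at n = 53 and 139.0% at n = 70. The 2.5% at a CV of 112% and n = 53 arises because the observed SD can fall below the true one.

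**The case against.** The best defence is context. Protocol 10.5.2 is headed as non-inferiority testing, and the same sentence names the margin. The hypotheses are exact in Protocol 10.1.2.3 and SAP 2.3.2.3. The plan also powers the test on "This assumes that the true geometric mean ratio between the two groups is 0.85 and the CV of TNA" NF50 is 100%, so it openly allows for a true 15% reduction. On that reading, the wording in 10.5.2 is shorthand for no reduction beyond the margin. The synopsis and SAP 7.2 already say non-inferior. SAP 7.1, 7.2 and 7.2.1 require GMTs, the ratio and adjusted ratios with CIs, so a careful reader would see the whole picture. The equivalence conclusions for PK (Protocol 10.5.1.2 and 10.5.1.3, SAP 6.5.1 and 6.5.2) use similar shorthand. The size of the problem depends on a CV that the documents assume and do not observe: at n = 53 the range in the observed ratio is only about 0.035 wide, and it vanishes near a CV of 112%.

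Most of this stands as a limit on weight. The endpoint is secondary and conditional on PK, nothing would be hidden, and the frequency is sensitive to the CV in both directions. It does not make the wording correct. The conclusion in 10.5.2 omits the qualifier, and the synopsis and SAP 7.2 go past non-inferiority to a further inference that the test does not support. That overreach is present at any CV; the CV only decides how often the CI would openly contradict it. The similar PK shorthand does not justify this wording.

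**Conclusion.** The concern holds. As written, the plan permits a conclusion of no reduction, or of no demonstrable effect, from a result that excludes only a reduction of 50% or more. Its own CI can contradict that conclusion. Under the plan's assumptions (log-normal NF50, CV 100%, equal variance, true ratio 0.85) the contradiction arises in about 7% of trials per antibiotic with 53 evaluable per group and about 17% with 70, conditional on the PK endpoint being met. The chance is larger if the CV is below 100% and becomes negligible at n = 53 once the CV is well above 112%. The fault lies in the permitted claim, not in the data, test, margin or sample size. It should be corrected, but it does not threaten the trial.

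**What to change.** Keep the margin, test and sample size, and change four sentences.

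- Protocol 10.5.2: reword the conclusion so that a lower limit above 0.5 means *non-inferior: a reduction in GMT of 50% or more is excluded*.
- Protocol synopsis (the ciprofloxacin and the doxycycline sentence) and SAP 7.2: these already say non-inferior, so replace only the closing inference about no demonstrable effect with *ie, a reduction in GMT of 50% or more is excluded*.

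Optionally add to SAP 7.2: *The GMT ratio and its full two-sided 95% CI will be reported beside the non-inferiority conclusion. A CI lying wholly below 1 will be described as such, descriptively and without a further formal test; if the primary PK endpoint is not met, all of this is for information only.*

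No decision rule on the upper limit should be added. Protocol 10.8 states "No other formal hypothesis testing will be carried out" and SAP 4.8 says the same. With no true effect, a CI wholly below 1 would still occur in 2.5% of trials per antibiotic, which is why the added sentence must stay descriptive. The cost is a slightly narrower permitted claim; nothing changes in data collection, power or pass/fail results.
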